# Figure 1: Study Design and Treatment Schema

# Table 3:Time and Events Schedule

Assessment	Screening	T (Every )	TreatmentBoosters(Every 3-Week Dosing)(Every 3-Month Dosing)							End of Study	Post Study Follow Up		
Study Week	Day -28 to -1	Baseline/ 0	3	6	9	18	21	30	33	42	45		
Clinic Visit	X	Х	Х	Х	X	Х	X	Х	Х	Х	X	Х	
Informed Consent	X												
Inclusion/Exclusion	X												
Demographics	X												
Physical Examination, Height a , Weight, ECOG	X b	X b	X	X	X	X		Х		X		X	
Medical History c	X	Х											
Confirm HER2 Expression d	X												
Concomitant Medications	X	Х	Х	Х	X	Х		Х		Х		Х	
Vital Signs e	X	Х	Х	Х	X	Х		Х		Х		Х	
12-Lead ECG	X				X	Х		Х		Х		Х	
Echocardiogram/MUGA f	X				X	Х		Х		Х		Х	
Confirm Contraceptive Measures g	X												
Study Drug Injection/ Injection Site Reaction Monitoring h		X	X	Х		X		Х		X			
Dispensation of Subject Diary Card i		X	Х	Х		X		Х		X			

Confidential and Proprietary

# ETBX-021 Clinical Trial Protocol: CMS-005 Amendment 1

Assessment	Screening	T (Every )	Treatment Boosters (Every 3-Week Dosing) (Every 3-Month Dosing)							End of Study	Post Study Follow Up		
Study Week	Day -28 to -1	Baseline/ 0	3	6	9	18	21	30	33	42	45		
Review of Subject Diary Card i			Х	Х	Х		X		Х		X	X	
Telephone Contact 72 Hours Post Injection		X	X	X		X		X		Х			
Tumor Imaging j	X				Х	X		X		Х		X	
Pregnancy Test k	X b	X b	Х	Х		X		X		Х		X	
Urinalysis	X				Х			X				X	
Chemistry Panel	X b	X b	Х	Х	Х	X		X		Х		X	
CBC, Differential, Platelets	X b	X b	Х	Х	Х	X		X		Х		X	
Coagulation	X				Х					Х		X	
Serum Virology (HIV, HBV, HCV) 	X												
Adverse Events		Х	Х	Х	Х	X	X	X	Х	Х	X	Х	
Exploratory Immune Analysis		X	X	Х	X	Х	Х	X	Х	Х	Х		
Exploratory Genomics and Proteomics Molecular Analysis	X												
Telephone Follow Up m													Х

# **PROTOCOL SYNOPSIS**

# Name of Sponsor/Company:

NantBioScience, Inc.

# Name of Investigational Product:

Ad5 [E1-, E2b-]-HER2/neu Vaccine, Suspension for Injection (ETBX-021)

## Name of Active Ingredient:

Ad5 [E1-, E2b-]-HER2/neu

## Title of Study:

Phase I Study of Ad5 [E1-, E2b-]-HER2/neu Vaccine (ETBX-021) in Subjects with Unresectable Locally Advanced or Metastatic HER2-Low-Expressing (IHC 1+/2+) Breast Cancer

#### Study Number:

CMS-005

## Study Phase:

Phase I

#### Primary Objectives:

• Determine the overall safety and recommended phase 2 dose of ETBX-021 when administered subcutaneously (SC) every 3 weeks for three injections followed by three booster injections at 3-month intervals to subjects with HER2-low-expressing breast cancer.

## **Secondary Objectives:**

• Make preliminary assessments of objective response rate (ORR), disease control rate (DCR), duration of response, progression-free survival (PFS), and overall survival (OS) in subjects with HER2-low-expressing breast cancer treated with ETBX-021.

## **Exploratory Objectives:**

• Evaluate the immunogenicity of ETBX-021 and determine the genomic and proteomic profile of subjects' tumors to identify gene mutations, gene amplifications, RNA-expression levels, and protein-expression levels. Correlations between genomic/proteomic profiles and efficacy outcomes will be assessed.

## **Primary Endpoints:**

- Dose-limiting toxicities (DLTs) and maximum tolerated dose (MTD) or highest tested dose (HTD).
- Treatment-emergent adverse event (AEs) and serious adverse events (SAEs).
- Clinically significant changes in safety laboratory tests, physical examinations, electrocardiograms (ECGs), left ventricular ejection fraction (LVEF), and vital signs.

## **Secondary Endpoints:**

- ORR (confirmed complete or partial response) according to the Response Evaluation Criteria in Solid Tumors (RECIST) Version 1.1.
- DCR (confirmed response or stable disease lasting for at least 6 months).
- Duration of response.
- PFS.

#### • OS.

# **Exploratory Endpoints:**

- Immunogenicity of ETBX-021 by flow cytometric analysis of T-cell frequency, activation status, cytokine profiles, and antibody levels.
- Genetic and proteomic profiling and correlations with efficacy.

# Study Design:

This is a Phase I trial in subjects with unresectable locally advanced or metastatic HER2-lowexpressing (IHC 1+ or 2+) breast cancer. The study will be conducted in two parts: the first part will involve dose escalation using a 3 + 3 design, and the second part will involve the expansion of the MTD or HTD to further evaluate safety, preliminary efficacy, and immunogenicity. In the first part, 3 to 6 subjects will be sequentially enrolled starting at dose cohort 1. Subjects will be assessed for dose-limiting toxicities (DLTs).

- Cohort 1:  $5 \times 10^{10}$  virus particles (VP).
- Cohort 2: 5 x 10^11 VP.
- If needed, dose de-escalation cohort (cohort -1):  $5 \times 10^9$  VP.

Dose expansion will occur when the MTD or HTD has been determined. An additional 12 subjects will be enrolled in the dose expansion component of the trial, for a total of 18 subjects at the MTD or HTD.

# **Enrollment (planned):**

Up to 30 subjects will be enrolled in the study. In the dose escalation component, 3 to 6 subjects will be sequentially enrolled starting at Cohort 1. In the dose expansion component (i.e., once the MTD or HTD has been identified), an additional 12 subjects will be enrolled for a total of 18 subjects in the MTD/HTD cohort to obtain further safety, preliminary efficacy, and immunogenicity data.

# Diagnosis and Main Criteria for Inclusion:

Subjects must have histologically confirmed unresectable locally advanced or metastatic breast cancer that expresses HER2 (IHC 1+ or 2+). Subjects with HER2 IHC 3+ tumors are excluded.

# Investigational Product, Dosage, and Mode of Administration:

ETBX-021 (5 x  $10^9$ , 5 x  $10^{10}$ , or 5 x  $10^{11}$  VP in 1.0 mL) will be administered by SC injection every 3 weeks for 3 injections, followed by 3 booster injections at 3-month intervals.

# **Duration of Treatment:**

Subjects will receive treatment for up to 42 weeks (injections at 0, 3, and 6 weeks with booster injections at 18, 30, and 42 weeks) or until they experience progressive disease or unacceptable toxicity, withdraw consent, or if the Investigator feels it is no longer in their best interest to continue treatment.

# Reference Therapy, Dosage, and Mode of Administration:

Not applicable.

# Criteria for Evaluation:

**Safety:** Safety endpoints include assessments of DLT, MTD or HTD, treatment-emergent AEs, SAEs, and clinically significant changes in safety laboratory tests, physical examinations, ECGs, LVEF, and vital signs. Toxicities will be graded using the National Cancer Institute (NCI) Common Terminology Criteria for Adverse Events (CTCAE) Version 4.03.

**Efficacy:** Tumor response (ORR and DCR) will be evaluated according to RECIST Version 1.1; duration of response, PFS, and OS will also be evaluated.

**Exploratory Immune Analysis:** Immune responses will be detected and quantified in flow cytometrybased and serum assays.

**Exploratory Molecular Profiling and Analysis and its Rationale:** Genomic sequencing of tumor cells from tissue relative to non-tumor cells from whole blood will be profiled to identify the genomic variances that may contribute to response or disease progression and provide an understanding of molecular abnormalities. RNA sequencing will be conducted to provide expression data and give relevance to DNA mutations. Quantitative proteomics analysis will be conducted to determine the exact amounts of specific proteins and to confirm expression of genes that are correlative of response to vaccine immunotherapy and disease progression. All genomic, transcriptomic, and proteomic molecular analyses will be retrospective and exploratory.

#### **Statistical Methods:**

The rate of DLTs and the MTD or HTD will be assessed. Overall safety will be assessed by descriptive analyses using tabulated frequencies of AEs by grade using CTCAE Version 4.03 within dose cohorts and for the overall study population in terms of treatment-emergent AEs, SAEs, and clinically significant changes in safety laboratory tests, physical examinations, ECGs, LVEF, and vital signs. ORR and DCR will be evaluated according to RECIST Version 1.1 by dose cohort and overall; duration of response will also be evaluated. PFS and OS will be analyzed using Kaplan-Meier methods by dose cohort and overall.

# Figure 1: Study Design and Treatment Schema

# Table 3:Time and Events Schedule

Assessment	Screening	T (Every		(Ever	End of Study	Post Study Follow Up							
Study Week	Day -28 to -1	Baseline/ 0	3	6	9	18	21	30	33	42	45		
Clinic Visit	X	X	Х	Х	Х	Х	X	X	Х	Х	Х	Х	
Informed Consent	Х												
Inclusion/Exclusion	X												
Demographics	Х												
Physical Examination, Height a , Weight, ECOG	X b	X b	Х	X	X	X		X		Х		X	
Medical History c	Х	Х											
Confirm HER2 Expression d	Х												
Concomitant Medications	X	X	Х	Х	Х	Х		X		Х		Х	
Vital Signs e	Х	X	Х	Х	Х	Х		X		Х		X	
12-Lead ECG	X				X	Х		X		Х		Х	
Echocardiogram/MUGA f	X				X	Х		X		Х		Х	
Confirm Contraceptive Measures g	X												
Study Drug Injection/ Injection Site Reaction Monitoring h		X	X	X		X		X		X			
Dispensation of Subject Diary Card i		X	X	X		X		X		Х			

Confidential and Proprietary

# ETBX-021 Clinical Trial Protocol: CMS-005 Amendment 2

Assessment	Screening	TreatmentBoosters(Every 3-Week Dosing)(Every 3-Month Dosing)							End of Study	Post Study Follow Up			
Study Week	Day -28 to -1	Baseline/ 0	3	6	9	18	21	30	33	42	45		
Review of Subject Diary Card i			Х	X	Х		Х		X		Х	X	
Telephone Contact 72 Hours Post Injection		X	X	X		X		X		X			
Tumor Imaging j	Х				Х	Х		Х		Х		Х	
Pregnancy Test k	X b	X b	Х	X		Х		Х		Х		X	
Urinalysis	Х				Х			Х				X	
Chemistry Panel	X b	X b	Х	Х	Х	Х		Х		Х		X	
CBC, Differential, Platelets	X b	X b	Х	X	Х	Х		Х		Х		X	
Coagulation	X				Х					Х		Х	
Serum Virology (HIV, HBV, HCV) 	X												
Adverse Events		X	Х	X	Х	Х	Х	Х	X	Х	Х	Х	
Exploratory Immune Analysis		X	Х	X	Х	Х	Х	X	X	Х	Х		
Exploratory Genomics, Transcriptomics, and Proteomics Molecular Analysis	X												
Telephone Follow Up m													X

# **PROTOCOL SYNOPSIS**

## Name of Sponsor/Company:

NantBioScience, Inc.

#### Name of Investigational Product:

Ad5 [E1-, E2b-]-HER2/neu Vaccine, Suspension for Injection (ETBX-021)

#### Name of Active Ingredient:

Ad5 [E1-, E2b-]-HER2/neu

#### Title of Study:

Phase 1 Study of Ad5 [E1-, E2b-]-HER2/neu Vaccine (ETBX-021) in Subjects with Unresectable Locally Advanced or Metastatic HER2-Expressing (IHC 1+/2+/3+) Cancer

#### Study Number:

QUILT-3.013 (formerly CMS-005)

#### **Study Phase:**

Phase 1

#### **Primary Objectives:**

• Determine the overall safety and recommended phase 2 dose of ETBX-021 when administered subcutaneously (SC) every 3 weeks for three injections followed by three booster injections at 3-month intervals to subjects with HER2-expressing cancer.

#### **Secondary Objectives:**

• Make preliminary assessments of objective response rate (ORR), disease control rate (DCR), duration of response, progression-free survival (PFS), and overall survival (OS) in subjects with HER2-expressing cancer treated with ETBX-021.

#### **Exploratory Objectives:**

• Evaluate the immunogenicity of ETBX-021 and determine the genomic and proteomic profile of subjects' tumors to identify gene mutations, gene amplifications, RNA-expression levels, and protein-expression levels. Correlations between genomic/proteomic profiles and efficacy outcomes will be assessed.

#### **Primary Endpoints:**

- Dose-limiting toxicities (DLTs) and maximum tolerated dose (MTD) or highest tested dose (HTD).
- Treatment-emergent adverse event (AEs) and serious adverse events (SAEs).
- Clinically significant changes in safety laboratory tests, physical examinations, electrocardiograms (ECGs), left ventricular ejection fraction (LVEF), and vital signs.

#### **Secondary Endpoints:**

- ORR (confirmed complete or partial response) according to the Response Evaluation Criteria in Solid Tumors (RECIST) Version 1.1.
- DCR (confirmed response or stable disease lasting for at least 6 months).
- Duration of response.
- PFS.
- OS.

# **Exploratory Endpoints:**

- Immunogenicity of ETBX-021 by flow cytometric analysis of T-cell frequency, activation status, cytokine profiles, and antibody levels.
- Genetic and proteomic profiling and correlations with efficacy.

# **Study Design:**

This is a phase 1 trial in subjects with unresectable locally advanced or metastatic HER2-expressing (IHC 1+, 2+, or 3+) cancer. The study will be conducted in two parts: the first part will involve dose escalation using a 3 + 3 design, and the second part will involve the expansion of the MTD or HTD to further evaluate safety, preliminary efficacy, and immunogenicity. In the first part, 3 to 6 subjects will be sequentially enrolled starting at dose cohort 1. Subjects will be assessed for dose-limiting toxicities (DLTs).

- Cohort 1:  $5 \times 10^{10}$  virus particles (VP).
- Cohort 2:  $5 \times 10^{11}$  VP.
- If needed, dose de-escalation cohort (cohort -1):  $5 \times 10^9$  VP.

Dose expansion will occur when the MTD or HTD has been determined. An additional 12 subjects will be enrolled in the dose expansion component of the trial, for a total of 18 subjects at the MTD or HTD.

# **Enrollment (planned):**

Up to 30 subjects will be enrolled in the study. In the dose escalation component, 3 to 6 subjects will be sequentially enrolled starting at cohort 1. In the dose expansion component (ie, once the MTD or HTD has been identified), an additional 12 subjects will be enrolled for a total of 18 subjects in the MTD/HTD cohort to obtain further safety, preliminary efficacy, and immunogenicity data.

# Diagnosis and Main Criteria for Inclusion:

Subjects must have histologically confirmed unresectable locally advanced or metastatic cancer that expresses HER2 (IHC 1+, 2+, or 3+).

# Investigational Product, Dosage, and Mode of Administration:

ETBX-021 ( $5 \times 10^9$ ,  $5 \times 10^{10}$ , or  $5 \times 10^{11}$  VP in 1.0 mL) will be administered by SC injection every 3 weeks for 3 injections, followed by 3 booster injections at 3-month intervals.

## **Duration of Treatment:**

Subjects will receive treatment for up to 42 weeks (injections at 0, 3, and 6 weeks with booster injections at 18, 30, and 42 weeks) or until they experience progressive disease or unacceptable toxicity, withdraw consent, or if the Investigator feels it is no longer in their best interest to continue treatment.

## Reference Therapy, Dosage, and Mode of Administration:

Not applicable.

# Criteria for Evaluation:

**Safety:** Safety endpoints include assessments of DLT, MTD or HTD, treatment-emergent AEs, SAEs, and clinically significant changes in safety laboratory tests, physical examinations, ECGs, LVEF, and vital signs. Toxicities will be graded using the National Cancer Institute (NCI) Common Terminology Criteria for Adverse Events (CTCAE) Version 4.03.

**Efficacy:** Tumor response (ORR and DCR) will be evaluated according to RECIST Version 1.1; duration of response, PFS, and OS will also be evaluated.

**Exploratory Immune Analysis:** Immune responses will be detected and quantified in flow cytometrybased and serum assays. **Exploratory Molecular Profiling, Analysis, and Rationale:** Genomic sequencing of tumor cells from tissue relative to non-tumor cells from whole blood will be profiled to identify the genomic variances that may contribute to response or disease progression and provide an understanding of molecular abnormalities. RNA sequencing will be conducted to provide expression data and give relevance to DNA mutations. Quantitative proteomics analysis will be conducted to determine the exact amounts of specific proteins and to confirm expression of genes that are correlative of response to vaccine immunotherapy and disease progression. All genomic, transcriptomic, and proteomic molecular analyses will be retrospective and exploratory.

## **Statistical Methods:**

The rate of DLTs and the MTD or HTD will be assessed. Overall safety will be assessed by descriptive analyses using tabulated frequencies of AEs by grade using CTCAE Version 4.03 within dose cohorts and for the overall study population in terms of treatment-emergent AEs, SAEs, and clinically significant changes in safety laboratory tests, physical examinations, ECGs, LVEF, and vital signs. ORR and DCR will be evaluated according to RECIST Version 1.1 by dose cohort and overall; duration of response will also be evaluated. PFS and OS will be analyzed using Kaplan-Meier methods by dose cohort and overall.

# Figure 1: Study Design and Treatment Schema

# Table 3:Time and Events Schedule

Assessment	Screening	T (Every )		(Ever	End of Study	Post Study Follow Up							
Study Week	Day -28 to -1	Baseline/ 0	3	6	9	18	21	30	33	42	45		
Clinic Visit	X	Х	Х	X	X	X	X	Х	X	X	X	X	
Informed Consent	X												
Inclusion/Exclusion	x												
Demographics	X												
Physical Examination, Height a , Weight, ECOG	X b	X b	Х	X	X	X		Х		X		X	
Medical History c	X	Х											
Confirm HER2 Expression d	X												
Concomitant Medications	X	Х	Х	X	X	X		Х		X		X	
Vital Signs e	X	Х	Х	X	X	X		Х		X		X	
12-Lead ECG	X				X	X		Х		X		X	
Echocardiogram/MUGA f	X				X	X		Х		X		X	
Confirm Contraceptive Measures g	X												
Study Drug Injection/ Injection Site Reaction Monitoring h		X	Х	X		X		Х		X			
Dispensation of Subject Diary Card i		X	X	X		X		X		X			

Confidential and Proprietary

# ETBX-021 Clinical Trial Protocol: QUILT-3.013 (CMS-005) Amendment 3

Assessment	Screening	T (Every 3		(Ever	End of Study	Post Study Follow Up							
Study Week	Day -28 to -1	Baseline/ 0	3	6	9	18	21	30	33	42	45		
Review of Subject Diary Card i			Х	X	X		X		Х		Х	X	
Telephone Contact 72 Hours Post Injection		Х	Х	X		X		X		X			
Tumor Imaging j	X				X	Х		Х		Х		X	
Pregnancy Test k	X b	X b	Х	X		Х		Х		Х		X	
Urinalysis	X				X			Х				X	
Chemistry Panel	X b	X b	Х	X	X	Х		Х		Х		X	
CBC, Differential, Platelets	X b	X b	Х	X	X	Х		Х		Х		X	
Coagulation	Х				X					Х		X	
Serum Virology (HIV, HBV, HCV) 	X												
Adverse Events		Х	Х	X	X	Х	X	Х	Х	Х	X	X	
Exploratory Immune Analysis		Х	Х	X	X	Х	X	Х	Х	Х	Х		
Exploratory Genomics, Transcriptomics, and Proteomics Molecular Analysis	X												
Telephone Follow Up m													Х

# **PROTOCOL SYNOPSIS**

## Name of Sponsor/Company:

NantBio, Inc.

## Name of Investigational Product:

Ad5 [E1-, E2b-]-HER2/neu Vaccine, Suspension for Injection (ETBX-021)

## Name of Active Ingredient:

Ad5 [E1-, E2b-]-HER2/neu

#### Title of Study:

Phase 1 Study of Ad5 [E1-, E2b-]-HER2/neu Vaccine (ETBX-021) in Subjects with Unresectable Locally Advanced or Metastatic HER2-Expressing (IHC 1+/2+/3+) Cancer

#### Study Number:

QUILT-3.013 (formerly CMS-005)

#### Study Phase:

Phase 1

#### **Primary Objectives:**

• Determine the overall safety and recommended phase 2 dose of ETBX-021 when administered subcutaneously (SC) every 3 weeks for three injections followed by three booster injections at 3-month intervals to subjects with HER2-expressing cancer.

#### **Secondary Objectives:**

• Make preliminary assessments of objective response rate (ORR), disease control rate (DCR), duration of response, progression-free survival (PFS), and overall survival (OS) in subjects with HER2-expressing cancer treated with ETBX-021.

## **Exploratory Objectives:**

• Evaluate the immunogenicity of ETBX-021 and determine the genomic and proteomic profile of subjects' tumors to identify gene mutations, gene amplifications, RNA-expression levels, and protein-expression levels. Correlations between genomic/proteomic profiles and efficacy outcomes will be assessed.

## **Primary Endpoints:**

- Dose-limiting toxicities (DLTs) and maximum tolerated dose (MTD) or highest tested dose (HTD).
- Treatment-emergent adverse event (AEs) and serious adverse events (SAEs).
- Clinically significant changes in safety laboratory tests, physical examinations, electrocardiograms (ECGs), left ventricular ejection fraction (LVEF), and vital signs.

## **Secondary Endpoints:**

- ORR (confirmed complete or partial response) according to the Response Evaluation Criteria in Solid Tumors (RECIST) Version 1.1.
- DCR (confirmed response or stable disease lasting for at least 6 months).
- Duration of response.
- PFS.
- OS.

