# Enrollment (planned):

Up to 30 subjects will be enrolled in the study. In the dose escalation component, 3 to 6 subjects will be sequentially enrolled starting at cohort 1. In the dose expansion component (ie, once the MTD or HTD has been identified), an additional 12 subjects will be enrolled for a total of 18 subjects in the MTD/HTD cohort to obtain further safety, preliminary efficacy, and immunogenicity data.

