# Investigational Product, Dosage, and Mode of Administration:

ETBX-021 ( $5 \times 10^9$ ,  $5 \times 10^{10}$ , or  $5 \times 10^{11}$  VP in 1.0 mL) will be administered by SC injection every 3 weeks for 3 injections, followed by 3 booster injections at 3-month intervals.

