# **Duration of Treatment:**

Subjects will receive treatment for up to 42 weeks (injections at 0, 3, and 6 weeks with booster injections at 18, 30, and 42 weeks) or until they experience progressive disease or unacceptable toxicity, withdraw consent, or if the Investigator feels it is no longer in their best interest to continue treatment.

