# Criteria for Evaluation:

**Safety:** Safety endpoints include assessments of DLT, MTD or HTD, treatment-emergent AEs, SAEs, and clinically significant changes in safety laboratory tests, physical examinations, ECGs, LVEF, and vital signs. Toxicities will be graded using the National Cancer Institute (NCI) Common Terminology Criteria for Adverse Events (CTCAE) Version 4.03.

**Efficacy:** Tumor response (ORR and DCR) will be evaluated according to RECIST Version 1.1; duration of response, PFS, and OS will also be evaluated.

**Exploratory Immune Analysis:** Immune responses will be detected and quantified in flow cytometrybased and serum assays.

**Exploratory Molecular Profiling, Analysis, and Rationale:** Genomic sequencing of tumor cells from tissue relative to non-tumor cells from whole blood will be profiled to identify the genomic variances that may contribute to response or disease progression and provide an understanding of molecular abnormalities. RNA sequencing will be conducted to provide expression data and give relevance to DNA mutations. Quantitative proteomics analysis will be conducted to determine the exact amounts of specific proteins and to confirm expression of genes that are correlative of response to vaccine immunotherapy and disease progression. All genomic, transcriptomic, and proteomic molecular analyses will be retrospective and exploratory.

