#### **Statistical Methods:**

The rate of DLTs and the MTD or HTD will be assessed. Overall safety will be assessed by descriptive analyses using tabulated frequencies of AEs by grade using CTCAE Version 4.03 within dose cohorts and for the overall study population in terms of treatment-emergent AEs, SAEs, and clinically significant changes in safety laboratory tests, physical examinations, ECGs, LVEF, and vital signs. ORR and DCR will be evaluated according to RECIST Version 1.1 by dose cohort and overall; duration of response will also be evaluated. PFS and OS will be analyzed using Kaplan-Meier methods by dose cohort and overall.

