# Figure 1: Study Design and Treatment Schema

# Table 3:Time and Events Schedule

Assessment	Screening	T (Every)		(Ever	End of Study	Post Study Follow Up							
Study Week	Day -28 to -1	Baseline/ 0	3	6	9	18	21	30	33	42	45		
Clinic Visit	Х	X	Х	X	X	X	X	Х	X	Х	Х	X	
Informed Consent	Х												
Inclusion/Exclusion	X												
Demographics	Х												
Physical Examination, Height a , Weight, ECOG	X b	X b	X	X	X	X		X		X		X	
Medical History c	X	X											
Confirm HER2 Expression d	Х												
Concomitant Medications	Х	X	Х	X	X	X		Х		Х		X	
Vital Signs e	Х	X	Х	X	X	X		Х		Х		X	
12-Lead ECG	Х				X	X		Х		Х		X	
Echocardiogram/MUGA f	Х				X	X		Х		Х		X	
Confirm Contraceptive Measures g	Х												
Study Drug Injection/ Injection Site Reaction Monitoring h		X	X	X		X		Х		Х			
Dispensation of Subject Diary Card i		X	X	X		X		Х		X			

Confidential and Proprietary

# ETBX-021 Clinical Trial Protocol: QUILT-3.013 (CMS-005) Amendment 4

Assessment	Screening	T (Every 3		(Ever	End of Study	Post Study Follow Up							
Study Week	Day -28 to -1	Baseline/ 0	3	6	9	18	21	30	33	42	45		
Review of Subject Diary Card i			Х	Х	Х		Х		Х		Х	Х	
Telephone Contact 72 Hours Post Injection		Х	Х	Х		Х		Х		Х			
Tumor Imaging j	X				Х	Х		Х		Х		X	
Pregnancy Test k	X b	X b	Х	Х		Х		Х		Х		Х	
Urinalysis	X				Х			Х				Х	
Chemistry Panel	X b	X b	Х	Х	Х	Х		Х		Х		X	
CBC, Differential, Platelets	X b	X b	Х	Х	Х	Х		Х		Х		X	
Coagulation	X				Х					Х		X	
Serum Virology (HIV, HBV, HCV) 	X												
Adverse Events		Х	Х	Х	Х	Х	Х	Х	Х	Х	Х	X	
Exploratory Immune Analysis		Х	Х	Х	Х	Х	Х	Х	Х	Х	Х		
Exploratory Genomics, Transcriptomics, and Proteomics Molecular Analysis	X												
Telephone Follow Up m													Х

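### Does the disease control rate need a dating rule because its 6-month stable-disease threshold falls between the week-18 and week-30 scans?

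*Combined protocol and SAP*

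**What the plan says.** All references are to the Amendment 4 synopsis in the combined protocol and SAP.

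- Secondary Endpoints gives the definition: "DCR (confirmed response or stable disease lasting for at least 6 months". The line contains no start date, end date or week equivalent.
- Criteria for Evaluation supplies the standard: "Tumor response (ORR and DCR) will be evaluated according to RECIST Version 1.1". Statistical Methods repeats it: "ORR and DCR will be evaluated according to RECIST Version 1.1 by dose cohort and overall".
- Secondary Objectives sets the level of ambition: "Make preliminary assessments of objective response rate (ORR), disease control rate (DCR" and the remaining efficacy measures.
- In Table 3 (Time and Events Schedule) the "Tumor Imaging" row is marked at screening (Day -28 to -1), weeks 9, 18, 30 and 42, and End of Study. The row carries footnote j, whose text is not in the supplied document.
- Investigational Product, Dosage, and Mode of Administration describes three injections "followed by 3 booster injections at 3-month intervals". Duration of Treatment puts this in weeks: "injections at 0, 3, and 6 weeks with booster injections at 18, 30, and 42 weeks".
- Enrollment (planned) provides "for a total of 18 subjects in the MTD/HTD cohort", out of at most 30 in the study.

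**The concern.** SD is only observed at scans. Here the qualifying duration falls inside a 12-week interval with no scheduled scan, so the definition alone does not settle every subject. Someone stable at weeks 9 and 18 who is found to have progressed at week 30 could be called controlled (stable until progression was documented) or not controlled (last known stable at week 18). Two analysts could report different rates from the same data. The difference would run in one direction across subjects, and a confidence interval would not reveal it.

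Only the SD component is exposed, because a confirmed response counts whatever its duration. At stake is how a reader interprets one of five secondary endpoints, which is reported by dose cohort as well as overall.

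**Working it through.** The plan states no target, power or expected value for this endpoint, so there is no figure to reproduce. The check has four steps.

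**1. Where 6 months falls.** The boosters at weeks 18, 30 and 42 follow the week-6 injection at 12-week steps, so the plan treats 3 months as 12 weeks and 6 months as 24. By the calendar, 1 month = 365.25 / 12 / 7 = 4.348 weeks, so 6 months = 26.1 weeks. Both values lie between 18 and 30. Measuring from the screening scan does not change this: with a scan on Day -28, week 18 is 18 + 4 = 22 weeks and week 30 is 34 weeks from baseline.

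**2. Effect of the dating convention.** Subject A is stable at weeks 9 and 18 and progresses at week 30. Subject B is stable at weeks 9, 18 and 30 and progresses at week 42.

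| SD measured from – to | A | B |
|---|---|---|
| First dose – progression | 30 weeks, counts | 42 weeks, counts |
| First dose – last stable scan | 18 weeks, does not count | 30 weeks, counts |
| First stable scan – progression | 30 − 9 = 21 weeks, does not count | 42 − 9 = 33 weeks, counts |
| First stable scan – last stable scan | 18 − 9 = 9 weeks, does not count | 30 − 9 = 21 weeks, does not count |

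Subject A counts under one convention of the four. Under the last, even B fails, and week 42 becomes the first qualifying scan. Start date and end date both matter.

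**3. Size.** One subject is 1/18 = 5.6 points in the main cohort and 1/30 = 3.3 points at maximum enrolment. The documents give no progression-free survival figure, so the number of subjects like A is an assumption, shown as a range. With time from first dose, exponential survival S(t) = 0.5^(t/m) and scheduled scans only, the share is S(18) − S(30):

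| Median m (months) | 2 | 3 | 4 | 6 | 9 | 12 |
|---|---|---|---|---|---|---|
| S(18) − S(30), points | 14.7 | 18.1 | 18.6 | 16.9 | 13.9 | 11.6 |
| × 18 subjects | 2.6 | 3.3 | 3.3 | 3.0 | 2.5 | 2.1 |

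The curve shape matters. With a Weibull curve of the same medians, S(t) = 0.5^((t/m)^k), the gap is 9.5 to 13.1 points for k = 0.7 and 11.5 to 27.4 points for k = 1.5. In the other direction, suppose 10% of subjects are responders and half of the progressions between weeks 18 and 26.1 are caught off schedule. The exponential gap is then 0.9 × [S(18) − 0.5 × (S(18) − S(26.1)) − S(30)] = 6.8 to 10.6 points, or 1.2 to 1.9 of 18 subjects.

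**4. Against sampling error.** Three subjects out of 18 is the difference between 3/18 = 16.7% (exact 95% interval 3.6% to 41.4%) and 6/18 = 33.3% (13.3% to 59.0%). The two intervals overlap over most of their length.

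**The case for a change.** The strongest argument for acting is that the dependence is demonstrable and the remedy cheap: one sentence beside the definition giving the SD start, the SD end and the week equivalent, plus table lines showing SD separately and the number of subjects like A. Sampling error is visible in an interval and a definitional shift is not. In an escalation cohort of 3 to 6 subjects, one reclassified subject moves the rate by 1/6 = 17 to 1/3 = 33 points.

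The facts in that argument stand: the threshold does fall between scans, and the count does depend on the dating. What does not stand is the step to a defect in the plan. The supplied text consists of synopses and schedules, and a synopsis endpoint line does not usually carry a dating algorithm. The rule may be in RECIST 1.1, the protocol body or footnote j, none of which can be read here, and the footnote could also set windows or extra scans that narrow the gap. Text that is unavailable cannot be counted as missing. The extra table lines are a reporting preference. In cohorts of 3 to 6, any response-type percentage is too imprecise for the dating to alter what a reader should conclude.

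Part of the information is also reported elsewhere. Statistical Methods plans Kaplan-Meier progression-free survival by dose cohort and overall. If progression is dated when it is detected, the subjects found to have progressed at week 30 appear there as a drop, although not split by SD and response.

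**Conclusion.** No change is needed. This is a gap in a summary line that analysts fill by adopting one dating convention for SD and applying it throughout, under the criteria the synopsis already names.

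The effect is about 2 to 3 of 18 subjects under exponential progression-free survival with medians of 2 to 12 months, before responders and off-schedule scans are allowed for. Other curve shapes give about 2 to 5 (9.5 points × 18 = 1.7; 27.4 points × 18 = 4.9). These medians and shapes are assumptions. The firm figure is 5.6 points per subject at n = 18.

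Two considerations settle it. First, nothing in the supplied text tests the disease control rate or ties a decision to it; the synopsis calls the efficacy assessments preliminary. Second, choosing a convention would not produce a true 6-month rate. In the exponential model with scheduled scans only, dating from first dose to documented progression gives a count that exceeds the week-26 value by S(18) − S(26.1) = 8.0 to 13.5 points. Dating to the last stable scan falls short by S(26.1) − S(30) = 3.3 to 5.1 points. That limit comes from scanning every 12 weeks.

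The conclusion would weaken if the full protocol or a later analysis plan used this rate in a decision rule, or compared it with an external benchmark, without fixing how SD is dated.
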